# 3.5.2 Why buprenorphine/naloxone for rapid treatment initiation?

For this study, we choose to use buprenorphine/naloxone to initiate treatment. Buprenorphine, the active treatment agent in the buprenorphine/naloxone medication, is a partial mu-opioid receptor agonist with greater affinity than heroin, morphine or other prescription opioids (Johnson, Strain et al. 2003, Orman and Keating 2009, Hser, Evans et al. 2016). It provides anti-withdrawal and anti-craving effects for up to 36 hours on a single dose. As a partial agonist, the slower onset of effect diminishes the patient's perception of euphoria (Mammen and Bell 2009, Dennis, Naji et al. 2014), while its safety profile, long half-life and binding duration make it useful for both short term use, tapering, and long-term opioid maintenance (Soyka 2015). Effectiveness has been demonstrated across diverse samples (Thomas, Fullerton et al. 2014). The initiation of treatment with buprenorphine is safer than with methadone and unobserved induction is widely adopted and has been shown to be as safe as supervised initiation (Lee, Vocci et al. 2014). A recent Cochrane review showed no difference in retention at any duration with supervised compared to unsupervised dosing in retention in treatment at 1-month and at 3-month follow-up, no difference in abstinence at the end of treatment and no difference in diversion of buprenorphine (Saulle, Vecchi et al. 2017).

Study participants who will receive buprenorphine/naloxone will be provided with information, counseling, and support for selection of ongoing treatment options including methadone maintenance (MMT), extended-release naltrexone (XR-NTX), or continued treatment with buprenorphine/naloxone (Baser, Chalk et al. 2011, Hartung, McCarty et al. 2014).

#### 3.6 Study Timeline

As shown in the Table below, following start-up activities (approvals, hiring, training, and data collection preparations), recruitment activities (community awareness) will start in month 5 and implementation of the intervention will begin in month 6 and continue for 18 months.

Rapid Induction Implementation Timeline								
Month	Pre Start	1 to 3	4 to 6	7 to 12	13-18	19-24	25-30	31-36
IRB Approval and CR								
CRF Finalization								
CRF Programming								
Staffing								
Training Preparation				I				
Training								
Recruitment								
RI Screening (ave/week)				120 (5/wk)	120 (5/wk)	120 (5/wk)		
RI Enrollment (ave/week)				42 (1.8 /wk)	42 (1.8 /wk)	42 (1.8 /wk)		
TAU Screening (ave/week)				120 (5/wk)	120 (5/wk)	120 (5/wk)		
TAU Enrollment (ave/week)				42 (1.8 /wk)	42 (1.8 /wk)	42 (1.8 /wk)		
Baseline Assessment								
Assessment 1 Mth								
Assessment 6 Mth								
Quality Monitoring								

## 3.7 Study Measures

All interviews will be administered by experienced research assistants trained in the administration of the proposed assessments. Following confirmation of eligibility, the mobile research assistants will complete the baseline assessment (described below). The participant assessments in this research will be sharply focused on the valid and reliable measurement of its primary endpoints i.e. ongoing treatment engagement will be the primary endpoint on which the study is powered. We will also carefully compare the two groups with respect to the rate of continued opioid use and subsequent overdoses. All assessments will be completed by trained research staff (not clinicians) at baseline, and again at 1- and 6-month post-enrollment. We anticipate follow-up rates of 95% and 90% at Month 1 and 6, respectively. We anticipate that the assessments will take approximately 45 minutes to complete.

- Physical history and examination including a blood test to evaluate the liver function.
- Locator Data Collection: A detailed contact sheet (Locator Form) will be completed for all subjects as part
  of the baseline assessment. We will ask participants to provide contact information on themselves and at
  least three additional people with whom they are most likely to stay in contact. We will also ask about other
  places where participants might be able to be contacted in the future. Participants will provide consent for
  research staff to contact individuals whose contact information they provide. Contact information will also
  include e-mail addresses and mobile phone numbers for texting. The locator form will be updated at each
  scheduled assessment visit. In addition, participants will be asked to call or visit the research staff
  whenever they have updates to provide regarding changes in contact information.
- DSM-5 Substance Use Disorder Checklist: This form is a listing of the eleven DSM-5 criteria for substance use disorder. We will screen for opioids, cocaine, and alcohol as each are necessary for confirmation of inclusion and exclusion criteria. A score of 4-6 is considered moderate severity and from 7-11 is considered severe substance use disorder. An opioid use disorder score of 4 or greater will be required for study eligibility. Alcohol use disorder and benzodiazepine scores of 4 or greater will be exclusionary.
- A study specific questionnaire that includes:
  - Socio-demographic Questionnaire: This brief questionnaire will be administered by research staff and will collect demographic information (e.g. age, gender, race and ethnic identity, marital status, sexual orientation, educational level, employment status, income and income sources) and descriptive information about the subject's living situation and housing stability, history of involvement with the criminal justice system, drug use, and drug treatment history.

- Addiction Severity Index (ASI) sections for Drugs and Alcohol and Medical Status: The ASI is a structured interview developed to assess the range of problems seen in drug users. The ASI produces severity ratings and composite scores in each of seven areas, and each type score has been assessed with regard to validity and reliability. Severity ratings and composite scores have demonstrated high levels of inter-rater, test-retest, and concurrent reliability (Cacciola et al., 2008; McLellan, Cacciola, Alterman, Rikoon, & Carise, 2006; McLellan et al., 1992). The Medical and the Drug and Alcohol sections will be administered at baseline, 1- and 6-month follow-ups.
- Patient Health Questionnaire (PHQ-9): Given the important role of depression in accessing and adhering to treatments for substance use disorder and other chronic medical problems (Mahajan, Avasthi, Grover, & Chawla, 2014; Tavakkoli, Ferrando, Rabkin, Marks, & Talal, 2013), we will also assess severity of depression using the 9-item Patient Health Questionnaire (PHQ-9). This brief assessment asks participants to indicate the frequency of occurrence of each of the nine DSM-IV diagnostic criteria for depression during the previous two weeks. This instrument has been widely used in clinical research and has strong psychometric properties. The PHQ-9 will be completed at baseline and months 1 and 6.
- Urine drug screen: We will use the CLIA waived® ACON Dip-and-Read 8-panel test for THC, cocaine, opiates, amphetamines, PCP, methamphetamine, benzodiazepines, barbiturates, and buprenorphine. The urine sample will be provided using standard procedures with temperature monitoring to preclude tampering and dilution.
- HIV testing: Chembio SURE CHECK HIV 1/2® rapid-HIV test kits will be used to detect antibodies. These FDA approved and CLIA Waived kits produce results in 15 minutes from a blood drop. For those who test antibody positive, additional blood will be drawn for confirmatory testing via RNA viral load assay. We anticipate that approximately 10% of participants will test positive for HIV.
- Economic evaluation: The cost-effectiveness of the intervention will be performed using data collected with questionnaires widely used for cost-effectiveness analyses.

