#### Rapid initiation of BUP/NX Version 1: Nov-15-2018

months. More than 90% of those who remained in treatment at 12 months were opiate-abstinent (Bachhuber, Thompson et al. 2018). Importantly, and in contrast to many other programs in the City, the STEP program has a waiting list of nearly 200 individuals.

The proposed project incorporates the concept of rapid initiation of MAT and consequently, the rapid control of withdrawal symptoms. A mobile team (Nurse Practitioner, Certified Peer Recovery Specialist, and a Case manager) will provide medication, counseling and treatment engagement support for one month. During this time, individuals will be linked to community MAT providers with unused capacity.

We will determine the economic value of the mobile intervention relative to treatment as usual from the perspective of the City of Philadelphia's Department of Public Health. [name], a Health Economist in the HIV Prevention Research Division, Department of Psychiatry, Perelman School of Medicine at the University of Pennsylvania, will lead this portion of study activities with consultations with colleagues at the Center for Health Economics of Treatment Interventions for Substance Use Disorder, HCV, and HIV (CHERISH). The results of this analysis will inform future policy decisions regarding implementation of this novel, mobile strategy for rapid initiation of MAT as a method for engagement in long-term evidence-based treatment. If the intervention in this study shows positive economic value, the City of Philadelphia's Department of Public Health may scale-up the intervention to reach more people throughout the city that may be at risk of opioid overdose. Enhanced interventions may require a greater amount of resources than alternative methods of more basic interventions or the usual standard of care. However, resource-intensive interventions may be justified through the achievement of better outcomes resulting from administering enhanced procedures.

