Analyses for Aim 3: We will estimate the total costs and per-participant costs of rapid initiation of MAT for opioid treatment engagement and use a cost-offsets approach to determine the economic value of this novel strategy. A cost-offsets approach requires a comparison of the total cost of the intervention (proposed enhanced procedure or treatment as usual) to the future costs of healthcare utilization avoided (i.e., benefits) due to the intervention. Healthcare utilization and medical costs will be estimated before and after participants receive either rapid initiation of MAT for opioid treatment engagement or treatment as usual. Information on healthcare utilization will be collected from participants at each assessment when study-staff administer the Non-Medical and Other Services Form (NSMOS; detailed description in Instruments section). Medical costs associated with these treatments/services will be estimated using Medicaid data. Costs of the intervention will be collected by [name], using the Drug Abuse Treatment Cost Analysis Program (DATCAP; detailed description in instruments section). She will interview staff in order to collect information on economic resource and cost variables such as staff salaries and benefits, study supplies and materials, major equipment, contracted services. building and facilities, and miscellaneous resources and costs. Recognizing that full-time staff members may devote only part of their work time to the proposed study, she will conduct a time-in-motion study with relevant study staff in order to track their time devoted to this study. Adjustments will then be made to salaries and benefits to reflect appropriate compensation attributed to this study. Similar adjustments will be made to reflect the time that some equipment, buildings and facilities, and miscellaneous resources and costs are attributed to the proposed study.

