Differences in pre-post medical costs will be used as an estimate of the value of downstream costs avoided due to the intervention. We will compare these differences across groups for statistical significance. We hypothesize that the medical costs after the intervention will be significantly lower for the participants that receive rapid initiation of MAT for opioid treatment than for the participants that receive treatment as usual. The economic value of this novel intervention will be positive if the costs of this novel intervention are outweighed by the medical cost savings that result from participants obtaining long-term and consistent opioid treatment. The proposed intervention is expected to aid with this process. Therefore, we hypothesize that the cost of rapid initiation of MAT for opioid treatment will be outweighed by the resulting avoidance of healthcare utilization costs.

We conduct our cost analyses from the perspective of the City of Philadelphia Department of Public Health since they may decide to scale-up the proposed services for other Philadelphia residents at risk of substance use overdose. Thus, we focus on healthcare utilization costs avoided as benefits of the proposed services. We may extend our analysis later to use a societal perspective that would consider other economic costs, such as criminal justice costs, unemployment costs, and participant costs (e.g., travel, work time missed, childcare expenses, etc.). Inclusion of the economic costs avoided due to opioid use disorder treatment will make the economic value of the proposed intervention even more positive than it is hypothesized to be when considering only healthcare utilization costs avoided due to opioid use disorder treatment.

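### Section 3.7 commits to cost-effectiveness, but the Aim 3 analysis specifies only a cost-offset, so no cost per additional person engaged is planned

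*Combined protocol and SAP*

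**What the plan says.** Three parts of the combined protocol and SAP bear on the economic evaluation.

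- **Section 3.7, Economic evaluation**, introduces the two cost instruments (DATCAP for program cost, NSMOS for service use) with this commitment: "The cost-effectiveness of the intervention will be performed using data collected with questionnaires widely used for cost-effectiveness analyses".
- **Sections 3.1 and 3.8.2** both give the rationale that "resource-intensive interventions may be justified through the achievement of better outcomes resulting from administering enhanced procedures". Both also say that the City may expand the program if its economic value proves positive.
- **Section 5, Analyses for Aim 3**, is the only place where a method is specified. The plan will "use a cost-offsets approach to determine the economic value of this novel strategy". Intervention cost is compared "to the future costs of healthcare utilization avoided (i.e., benefits) due to the intervention". Savings are measured as follows: "Differences in pre-post medical costs will be used as an estimate of the value of downstream costs avoided due to the intervention"; these differences are then compared between groups. The criterion is: "The economic value of this novel intervention will be positive if the costs of this novel intervention are outweighed by the medical cost savings". On what counts as benefit: "Thus, we focus on healthcare utilization costs avoided as benefits of the proposed services".

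The one extension mentioned is optional and adds only further cost items: "We may extend our analysis later to use a societal perspective that would consider other economic costs".

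**The concern.** A cost-effectiveness analysis relates incremental cost to an outcome. The Aim 3 text names no effectiveness measure, cost per outcome, net benefit or willingness-to-pay value. The analysis that Section 3.7 commits to therefore has no plan behind it.

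The rule that is specified also cannot express the rationale in Sections 3.1 and 3.8.2. Those sections describe a program that costs more and is worth it because outcomes are better. Under the Aim 3 criterion, such a program is positive only to the extent that the better outcomes turn into medical savings larger than the program cost.

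What is at stake is the economic result that the plan links to a possible scale-up by the City. If the mobile program improves engagement but leaves a net cost, the plan has no estimate, and no interval, that sets the gain against the cost.

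**Working it through.** **1. The plan's own figure.** The documents state no cost, saving or threshold. The only figure to reproduce is the effect size in Section 5.2: 125 per group, 80% power, 25% against 40% engagement, 80% completers, within-subject correlation 0.3. Two-sided 5% is assumed, since the text does not say.

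- One time point: n = [1.96·√(2·0.325·0.675) + 0.842·√(0.25·0.75 + 0.40·0.60)]² / 0.15² = 152 per group.
- Two repeated measures: factor (1 + 0.3)/2 = 0.65, so 152 × 0.65 = 98.8.
- Attrition: 98.8/0.80 = 123.5, so 124 against the stated 125. Power with 100 completers is 80.5%.
- RR = 0.40/0.25 = 1.6; OR = (0.40/0.60)/(0.25/0.75) = 2.0.

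The power statement reproduces. The 15 points is the detectable difference over months 1 and 6 together, not a forecast for month 6; it is used below only as a reference value.

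**2. What the rule contains.** Per participant, mobile minus treatment as usual (TAU), let C be incremental program cost, S medical savings and E the difference in the proportion engaged.

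- Aim 3 criterion: positive if S − C > 0.
- Cost-effectiveness ratio: (C − S)/E.

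E does not appear in the first expression. It can act only through S. Whenever C − S is above zero, the criterion is not met, whatever the size of E.

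**3. Direction of the indirect route.** Section 3.7 has the NSMOS record outpatient treatment days and medication for opioid use disorder. Section 4.4 excludes people currently in MAT. The Aim 3 text does not take MAT itself out of the costed utilization. Extra engagement can therefore raise measured utilization cost as well as lower it elsewhere; the net sign is not known in advance.

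**4. Size of the missing figure.** All dollar amounts are assumptions. Cost per additional person engaged = (C − S)/E:

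| Net cost per participant (C − S) | E = 10 points | E = 15 points | E = 20 points |
|---|---|---|---|
| $250 | $2,500 | $1,667 | $1,250 |
| $500 | $5,000 | $3,333 | $2,500 |
| $1,000 | $10,000 | $6,667 | $5,000 |
| $2,000 | $20,000 | $13,333 | $10,000 |

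At $3,000 and 15 points the figure is $20,000. The Aim 3 criterion treats every one of these cases alike.

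**5. Precision.** The plan counts missing participants as not engaged, so all 125 per group enter. The standard error of a 15-point difference is √(0.25·0.75/125 + 0.40·0.60/125) = 0.0585, and 15 ± 1.96 × 5.85 gives 3.5 to 26.5 points. With net cost held at an assumed $3,000, $3,000/0.265 = about $11,300 and $3,000/0.035 = about $85,700. This takes no account of propensity adjustment or of uncertainty in cost.

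**The case against.** The strongest defense is that the commitment is one sentence introducing two cost instruments. Aim 3 itself covers acceptability and costs, Section 3.8.2 calls the endpoint a cost evaluation, a payer perspective is stated, and the reference list includes cost-offset studies. A cost-offset looks deliberate, and relabeling Section 3.7 would be the smallest repair. That is fair as far as the label goes. It would still leave Sections 3.1 and 3.8.2 relying on a justification that no planned analysis examines.

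Several stronger readings are tempting and should not be drawn:

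- *The plan would report the program as having no economic value.* Section 5 says only when value is positive. It does not equate the opposite result with no value, and it does not say that the City would then decline to expand.
- *Engagement is given no value at all.* It counts indirectly, because the plan expects savings to follow from sustained treatment.
- *Nothing else would be reported.* Total and per-participant costs, cost differences by group and engagement by group are all planned. A reader could form a crude ratio, though without propensity adjustment or an interval.
- *Each additional engaged participant must save 1/0.15 = 6.7 times the program cost.* This assumes that all savings come from the extra engaged participants. Everyone in the mobile group is offered medication, peer support and case management, so others may save too. The relevant cost is also the increment over TAU, not the program cost.

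Two practical objections also stand in part. The Aim 3 text includes TAU in its definition of intervention cost, but the interviews and time tracking it describes cover study staff, while Section 4.9.1 has BAC/CRC staff delivering TAU engagement services. And the documents supply no willingness-to-pay value for an acceptability curve.

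**Conclusion.** The concern holds in this form: Section 3.7 commits to cost-effectiveness and Sections 3.1 and 3.8.2 appeal to better outcomes, but the only specified analysis is a cost-offset with no outcome term and no cost per outcome. A program that raises engagement at a net cost would be classed as not positive, with no planned estimate of what the gain cost.

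This conclusion rests on the text and does not depend on the dollar figures, which illustrate scale only. They do not show that a modest net cost is likely. The consequence is confined to Aim 3; the primary endpoint, its power and safety monitoring are untouched. Utilization is collected only up to month 6, and a month-6 ratio would keep that horizon rather than cure it.

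**What to change.** 1. In Section 5, Analyses for Aim 3, keep the cost-offset and add the incremental net cost (mobile minus TAU) per additional participant engaged in MAT at month 6. Use the same propensity strata as the primary analysis, and give bootstrap intervals for cost, effect and their ratio.
2. Confirm that the costing also covers the TAU engagement services delivered by BAC/CRC staff.
3. State beside the Aim 3 criterion that the cost-offset shows a net saving or a net cost, to be read together with the cost per additional person engaged.
4. If an acceptability curve is shown, draw it over a stated range of assumed willingness-to-pay values.

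The cost is wording plus one analysis built on DATCAP, NSMOS and the primary endpoint. Some additional cost collection at the BAC/CRC sites is needed if item 2 shows a gap. The downside is one more secondary result, probably an imprecise one, as the interval in the working shows. Relabeling Section 3.7 alone would settle the terminology but not supply the missing estimate.

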  - Non-Medical and Other Services Form (NSMOS): This questionnaire was adapted from the Treatment Services Review (McLellan et al., 1992; Cacciola et al., 2008) for patients receiving substance abuse treatment. It is designed to capture all medical and social services received by the participant between study visits. The NSMOS counts substance abuse treatment, medical services, employment visits, legal services, family services and psychological/emotional. It takes 5 to 10 minutes to complete. The Non-Medical and Other Services Form (NSMOS) will be used to collect information from participants on

their healthcare utilization. This information will enable us to estimate costs incurred by the City of Philadelphia's Department of Public Health. Participants will be asked about the medical services and other relevant resources they have utilized between assessments. More specifically, participants will be asked about: visits and number of visits to an emergency room (not admitted to hospital); admittances (number and duration) to hospitals to detoxify from drugs or alcohol, or for other reasons; participation and number of days in outpatient treatment program for drug or alcohol problems; admittance (number and duration) in a residential program to detoxify or for other services; receipt, type, and prescribed dose, of medication to treat alcohol use disorder, opioid use disorder, or mental health disorder; care (number of times) received by a psychiatrist or psychologist, counselor or social worker; number of visits to a medical office and number of visits with a doctor; amount spent out of pocket on healthcare (including prescriptions); and coverage and type of health insurance. Study staff will administer this form at each assessment. Time to complete will vary by participant.

